As part of its operation, the device captures photographs and video of the patient's eyes (figure 3). In addressing the secondary goal of potential correlation between eye behavior and clinical events, we will explore this possibility by evaluating photographs of the eyes at the times of clinical events (i.e. hypoxia, new onset shock, or new onset sepsis). The device will activate the image data collection only after 50 consecutive frames of eye-in-the-image. This should be a safety index to verify that the device is only recording the eye. It will stop recording immediately when non-eye-in-the-image occurs. Data processing to decide if an eye is in the image is done locally on the device, so eventually only images of eyes should be collected. All external image data processing will be done following deidentification of the data, using the patient code only as an identifier.

Figure 3. Example photographs captured by the EyeControl device.

No randomization or blinding is planned for this step of the study, and no samples are planned to be collected.

---

**STEP 2: MEASURE REDUCTION IN DELIRIUM-FREE AND ALIVE DAYS IN THE ICU WITH EYECONTROL-BASED COMMUNICATION COMPARED WITH THE STANDARD OF CARE.**

The second step will be similar to the operation of the first one, in terms of patient screening and enrolling. The main difference will be the randomization process. Patients will be randomized to use EyeControl for as much as they wish, versus the standard of care. Randomization will be done centrally, and will be stratified to the specific unit, gender and age, race and ethnicity.

The primary goal of the second step will be to measure the time spent alive and non-delirious in the ICU with EyeControl-based communication compared with the standard of care. Delirium will be defined as CAM-ICU positive, starting at day 1 of use (following the day of training), up to 14 days from randomization or ICU discharge, the earliest. However, patients could require moderate to deep sedation following randomization, for example due to new or evolving medical complication. Whenever the RASS is below (-1), CAM-ICU will not be measured, and will be charted as undetermined. Therefore, only days in which the patient will be CAM-ICU positive, will be counted towards the primary outcome. CAM-ICU positive days prior to randomization will not be counted towards the primary outcome.

[figure not shown]
The secondary outcomes will include the following:

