## SAMPLE SIZE

From our retrospective analysis (described in the introduction), we expect about 130 patients per month for the initial screening (ventilated for at least two days). The same patient could be ineligible on a certain day, but become eligible later in the admission (e.g., due to the severity of the illness, the patient is deeply sedated for the first few days, and later sedation is weaned). This will allow us to recruit more patients, at different time points of their admission. Even with this in mind, it would be reasonable to assume that about half of these initially screened patients will not be eligible at any point of their admission due to any one of the exclusion criteria. Of those who will be eligible, we expect a high rate of consent, due to the low risk and the potential benefit of using the device while in the ICU. We therefore expect a rate of about 30 patients a month to be enrolled.

For the first step, we will plan to enroll up to 60 patients, and at least a third of the sample will be from the neuroscience ICU, and specifically patients with an acute brain injury

Given that there are no prior data, there is no clear criteria that would justify a specific number. We believe that having 40 to 60 patients work with this new device would be sufficient to draw initial conclusions about its use and specific indications according to the study aims as stated above.

For the second part of the trial, power calculations are based on previously published BRAIN-ICU trial. In that observational trial patients had  $6.8 \pm 5.2$  delirium/coma-free days within the first 14 days of admission, with an overall rate of about 50% rate of delirium. For the present trial, we considered a 2 day reduction in the time spent delirious as clinically significant. Given these parameters, the present trial will require 248 patients ( $N = 124$  per arm) to achieve sufficient power (80%,  $\alpha = .05$ ) to detect a 2 day difference. In general, a sample size of 248 will provide sufficient power to detect a standardized mean difference of 0.38 (assuming minimal asymptotic relative efficiency of Mann-Whitney U test), an odds ratio of 2.14 for binary variables (assuming maximal variance for a binomial distribution), and a Cohen's  $f$  of 0.18.

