### Step 2:

Primary Outcome: The time spent alive and non-delirious in the ICU

Covariates/Confounders: age, gender, race, baseline education level, unit to which the patient was admitted to, need for tracheostomy, severity of illness by SOFA or APACHE score on admission and randomization day, categorical reason for admission (e.g. sepsis, ARDS, elective surgery, stroke etc), diagnosis of delirium prior to randomization and the presence of an acute central neurological injury.

Unadjusted Analyses: The time spent alive and non-delirious in the ICU will be evaluated using the stratified variant of the Mann-Whitney U test. In this analysis, patients will be stratified by ICU setting. For other variables, the unadjusted comparison will depend on the type of variable. In general, continuous variables will be compared using a Mann-Whitney U test and categorical variables will be compared using the  $\chi^2$  test.

Adjusted Analyses: The time spent alive and non-delirious in the ICU will be evaluated using a multi-level/mixed-effects quantile regression (median/50th percentile) while controlling for the previously listed covariates. The multi-level/mixed-effects model will be used to account for clustering within ICU setting. In the event that the regression fails to estimate properly, the covariates will be used to generate propensity scores and patients will be stratified into  $\geq 5$  propensity score strata. The time spent alive and non-delirious in the ICU will then be analyzed using the stratified variant of the Mann-Whitney U test. Analyses of the secondary outcomes will depend on the type of variable. Continuous variables will be analyzed using multi-level/mixed-effects quantile regressions (median/50th percentile), binary variable will be analyzed using multi-level/mixed-effects binary logistic regressions, ordinal scales will be analyzed using multi-level/mixed-effects ordinal (cumulative logit) logistic regressions.

Missing Data: In the event of substantial missing data, data will be imputed using a multiple imputation procedure. The type of procedure (e.g. fully conditional specification, hot decks etc.) and the number of imputed data sets will be determined by the amount of missing data and the pattern of missingness.

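### Unadjusted between-arm tests of outcomes other than the primary leave out the ICU unit used to stratify randomization; if units differ on those outcomes, the tests are conservative and lose some power

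*Combined protocol and SAP*

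**What the plan says.** The Step 2 design section sets the allocation: "Randomization will be done centrally, and will be stratified to the specific unit, gender and age, race and ethnicity".

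The Statistical Analysis Plan, Step 2, Unadjusted Analyses, names a stratified Mann-Whitney test for the primary outcome and adds: "In this analysis, patients will be stratified by ICU setting". It then turns to other variables: "In general, continuous variables will be compared using a Mann-Whitney U test and categorical variables will be compared using the" chi-square test. ICU is not mentioned for these, and no reason is given for the different rule.

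The Adjusted Analyses paragraph covers secondary outcomes separately. "Continuous variables will be analyzed using multi-level/mixed-effects quantile regressions" at the median, binary outcomes by mixed-effects logistic regression, and ordinal scales by mixed-effects cumulative logit. Of the multilevel model for the primary outcome it says: "The multi-level/mixed-effects model will be used to account for clustering within ICU setting". Unit is also on the covariate list. The plan does not say whether the adjusted or the unadjusted result leads for secondary outcomes.

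**The concern.** When allocation is balanced within units, differences between units largely cancel out of the comparison of arms. A test that ignores unit still counts them in its standard error, so the error is overstated and the test rejects too rarely. The primary test avoids this and the other unadjusted tests do not.

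The units run from medical and surgical to cardiac and neuroscience, and the plan itself treats neurologically injured patients as a distinct group. It is plausible, though not shown, that cognition, function and discharge destination differ by unit. At stake is some sensitivity in the unadjusted secondary comparisons, and consistency with the primary test.

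**Working it through.** **Inputs from the documents.** Power 80%, alpha 0.05 (sidedness not stated), difference 2 days, SD 5.2 days, 124 per arm (Sample Size); six unit types with 17, 23, 40, 20, 14 and 28 beds (Table 1).

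**Assumed.** The share R² of outcome variance that lies between units: 5%, 10% and 20%. The documents give no figure.

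**The plan's own figure.** A two-sided t test with effect 2/5.2 = 0.385 SD needs 107.1 per arm. Dividing by 0.864, the minimal asymptotic relative efficiency of the Mann-Whitney test, gives 123.9, so 124 per arm and 248 in all. The detectable standardized difference is (1.96 + 0.84) × √(2/(124 × 0.864)) = 0.38. Both match the plan, so the sample size is not in question.

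**Leaving unit out.** With balance within units, the true variance of the arm contrast is (1 − R²) times the variance that the unstratified test uses. Normal approximations, with 2.80 = 1.96 + 0.84 as the effect at which a stratified test has 80% power:

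- Type I error = 2[1 − Φ(1.96/√(1 − R²))]
- Power = Φ(z), where z = 2.80 − 1.96/√(1 − R²)
- Equivalent patients lost = 248 × (1 − [(1.96 + z)/2.80]²)

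| R² | 1.96/√(1 − R²) | Type I error | z | Power | Sample-size ratio | Patients |
|---|---|---|---|---|---|---|
| 5% | 2.011 | 4.4% | 0.791 | 78.5% | 0.964 | 9 |
| 10% | 2.066 | 3.9% | 0.736 | 76.9% | 0.926 | 18 |
| 20% | 2.191 | 2.8% | 0.610 | 72.9% | 0.842 | 39 |

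**Simulation, continuous outcome.** Six units sized by bed share, 1:1 within unit, 246 patients after rounding, normal outcomes, effect 0.385 of the total SD, 6,000 runs. Here the effect is fixed in total SDs, so the stratified test's power rises with the intraclass correlation (ICC); compare the two power columns within a row.

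| ICC | Type I, plain | Power, plain | Power, van Elteren |
|---|---|---|---|
| 0 | 5.3% | 84.1% | 83.2% |
| 0.02 | 5.1% | 83.9% | 83.3% |
| 0.05 | 4.7% | 84.4% | 85.1% |
| 0.10 | 3.9% | 84.7% | 86.5% |
| 0.20 | 3.0% | 86.6% | 91.0% |
| 0.30 | 2.1% | 87.6% | 94.2% |

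Van Elteren type I error stayed between 4.7% and 5.3%.

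**Simulation, binary outcome.** Same units, within-unit odds ratio 2.14 (the plan's detectable value), 20,000 runs. Power of chi-square against Cochran-Mantel-Haenszel was 82.5% and 82.5% at latent ICC 0, 81.4% and 82.3% at 0.03, 78.8% and 81.1% at 0.07, 73.0% and 77.8% at 0.16, and 68.6% and 75.9% at 0.23. Chi-square type I error fell from 4.8% to 2.8% across that range.

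**The case against.** The strongest reply is that ICU is already handled. The sentence that names secondary outcomes prescribes mixed-effects models, and the unadjusted sentence speaks only of other variables, in general terms. A reader might infer that the secondary analysis as a whole ignores ICU; the documents do not support that. The reply does not close the point, however. The plan does not say which result leads, gives a fallback for a failed regression only for the primary outcome, and names no adjusted model for a nominal outcome such as discharge disposition.

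A reader might also infer that every secondary outcome is affected. Most are not. Ability to operate the device, length and intensity of use, device-recorded wakefulness and device-versus-clinician CAM-ICU agreement have no control-arm value, so no between-arm test exists to be made conservative.

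Nor can it be said outright that p-values are too large and power is wasted. That depends on how far units differ, which is unknown; at an ICC of 0 to 0.02 the stratified test was marginally weaker.

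Multiplying R² by 248 would suggest 12, 25 or 50 patients lost. On the power figures above, with balance within units, the loss is 9, 18 or 39.

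Finally, exact balance is idealized. There are five stratifying factors, and six-month outcomes exist only for survivors who are reached. As balance within unit weakens, type I error moves back towards 5% and power falls slightly further. With no balancing it is Φ(2.80 × √(1 − R²) − 1.96), or 78.0%, 75.7% and 70.7%. Gender, age, race and ethnicity are also strata and are left out of the unadjusted primary test too; that is a related gap and does not answer this one.

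**Conclusion.** The point holds as a minor, conditional one. As written, the unadjusted between-arm tests of outcomes other than the primary ignore a factor used in randomization and in the primary test. Any error is towards caution: false positives are not inflated, and the primary result and the sample size of 248 are unaffected.

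The size rests on the assumed R² and on near-balance within units. It runs from nothing (or a gain of under one point for the plain test) when units barely differ, through about 1.5 and 3 points of power at 5% and 10%, to about 7 points at 20%. The patient equivalents assume all 248 contribute; for six-month outcomes the proportions (about 4%, 7% and 16%) are the better guide.

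**What to change.** In Unadjusted Analyses, state that between-arm comparisons of secondary outcomes use the van Elteren test for continuous and ordinal outcomes and the Cochran-Mantel-Haenszel test for categorical ones (the general-association form for nominal outcomes), stratified by ICU unit at randomization as for the primary outcome. It would help to add a clause saying whether the adjusted or the unadjusted result leads for secondary outcomes.

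The cost is one sentence in the analysis plan. Unit is already recorded and trial conduct does not change. The downside is a very small loss of efficiency if units do not differ or if some contribute few patients.

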Study Population	Critically ill patients who are admitted to the ICU at Emory University Hospital (EUH) who require mechanical ventilation for at least two days and are awake enough and cooperative to attempt working with the communication device (defined as Richmond Agitation Sedation Scale (RASS) score of -1 to 1).
Enrollment / Duration	Step 1: 60 Patients, approximately 8 months – No Long-Term Outcomes Step 2: 244 Patients, approximately 12 months – With LTO extending to 6 months
Subject Inclusion	
 
• Intensive Care Unit (ICU) Admission
 
• Mechanically ventilated for at least 24 hours
 
• RASS between -1 to 1 at the time of screening (Note: minimal sedation is allowed including low-dose Fentanyl, Dexmedetomidine, Ketamine, Propofol, etc.)
 

Subject Exclusion	
 
• < 18 years of age
 
• Not admitted to the ICU
 
• Inability to follow commands during screening
 
• Known cerebral injury (acute or chronic) in the dominant hemisphere concerning for aphasia on clinical assessment
 
• Significant pre-existing neurologic (i.e., dementia and/or cognitive deficiencies), psychologic, or baseline communication challenges that would confound outcomes assessments (including hearing loss)
 
• Inability to blink or move eyes for any reason
 
• Prisoner or incarceration
 
• Inability or unwillingness to provide informed consent
 
• Unwillingness to be contacted for follow-up
 

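### If the adjusted median regression fails, the propensity-score fallback is a conservative test when the covariates predict the outcome, and it forgoes nearly all the power that direct adjustment would add

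*Combined protocol and SAP*

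**What the plan says.** The Statistical Analysis Plan, Step 2, gives two analyses of time alive and non-delirious in the ICU. The unadjusted one is a Mann-Whitney test stratified by ICU. The adjusted one is a mixed-effects median regression on a list of more than ten covariates, including ICU, prior delirium, SOFA or APACHE score and need for tracheostomy.

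The fallback belongs to the adjusted analysis only: "In the event that the regression fails to estimate properly", "the covariates will be used to generate propensity scores and patients will be stratified into" at least five groups, and the stratified Mann-Whitney test is run across those groups. The SAP does not define failure, fix the number of strata, mention a variance correction for the estimated score, or say which of the two analyses decides the trial.

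Treatment is assigned at random. The Step 2 part of Study Design and Methods states: "Randomization will be done centrally, and will be stratified to the specific unit, gender and age, race and ethnicity". The Sample Size section gives 124 patients per arm, which implies 1:1 allocation.

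**The concern.** Propensity strata are designed for non-randomized comparisons, where treatment depends on patient characteristics. Here the true probability of receiving the device is one half for everyone, so a score fitted to the covariates can only pick up chance imbalance.

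Two things follow. First, comparing patients within score strata removes the part of the sampling variation that comes from covariate imbalance, so the test statistic truly varies less. Second, the strata do not group patients by prognosis, so the spread of ranks within a stratum stays about as wide as in the whole sample. The test takes its null variance from that spread. When the covariates predict the outcome, the assumed standard error is therefore too large and the p-values are too large.

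At stake is efficiency. The purpose of adjusting a randomized comparison for prognostic covariates is to gain power, and this fallback gains almost none.

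**Working it through.** **1. The plan's own figure.** Inputs from Sample Size: SD 5.2 days, difference 2 days ("we considered a 2 day reduction in the time spent delirious as clinically significant"), 80% power, α = 0.05 (taken as two-sided), and "assuming minimal asymptotic relative efficiency of Mann-Whitney U test" (taken as 0.864, the theoretical minimum; the documents give no number).

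- Two-sample normal formula: 2 × (1.960 + 0.842)² × 5.2² / 2² = 106.1, so 107 per arm.
- Divided by the efficiency: 107 / 0.864 = 123.8, so 124 per arm and 248 in total. This matches "the present trial will require 248 patients".
- Power at 124 per arm is 80.4% with the efficiency penalty and 85.7% without it.

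The Synopsis gives 244 instead of 248. That needs reconciling but does not affect this point (244 gives 79.7%). The plan states no error rate or power for the fallback, so there is no such figure to reproduce.

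**2. Size expected from theory.** Let R² be the share of outcome variance explained by the covariates. If stratification removed all covariate imbalance while the test's variance stayed put, the null statistic would have SD √(1 − R²) instead of 1. The true two-sided error would be 2 × [1 − Φ(1.96 / √(1 − R²))]:

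- R² = 0: 1.96 / 1.000 = 1.96, giving 5.0%
- R² = 0.1: 1.96 / 0.949 = 2.07, giving 3.9%
- R² = 0.2: 1.96 / 0.894 = 2.19, giving 2.8%
- R² = 0.3: 1.96 / 0.837 = 2.34, giving 1.9%
- R² = 0.5: 1.96 / 0.707 = 2.77, giving 0.6%

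**3. Simulation.** There were 4,000 trials per setting, each with 248 patients allocated 1:1. The outcome was drawn with mean 6.8 and SD 5.2, then rounded and limited to 0–14 days; the 2-day shift was applied before rounding. There were 24 covariate terms (the category counts are an assumption), a logistic propensity score, five equal strata and the stratified Mann-Whitney test at two-sided 5%. The comparators were the ICU-stratified test and rank analysis of covariance on the same covariates with ICU as indicator terms. Monte Carlo error is about 0.3 points for type I error and 0.6 points for power.

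| Assumed R² | Fallback type I error | ICU-stratified type I error | Rank ANCOVA type I error | Fallback power | ICU-stratified power | Rank ANCOVA power |
|---|---|---|---|---|---|---|
| 0 | 5.1% | 5.3% | 4.9% | 79.3% | 82.6% | 79.9% |
| 0.1 | 3.5% | 4.8% | 4.6% | 79.8% | 82.0% | 83.1% |
| 0.2 | 3.1% | 5.3% | 5.0% | 79.8% | 80.6% | 85.9% |
| 0.3 | 2.5% | 4.9% | 5.2% | 82.9% | 82.5% | 90.8% |
| 0.5 | 0.8% | 5.0% | 5.0% | 85.4% | 81.9% | 97.0% |

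Gain over the ICU-stratified test:

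- At R² = 0.2, direct adjustment gains 85.9 − 80.6 = 5.3 points; the fallback changes power by 79.8 − 80.6 = −0.8.
- At R² = 0.3, direct adjustment gains 90.8 − 82.5 = 8.3 points; the fallback gains 82.9 − 82.5 = 0.4.

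**4. Sensitivity at R² = 0.3.** The variations were ten strata, 22 covariate terms, an unrounded outcome, randomization stratified by unit, sex and age, and a six-covariate score. Fallback type I error stayed at 2.2–2.7% and power at 80.6–84.8%, against 90.2–91.4% for direct adjustment. Separate simulations with 21 covariate columns and six ICUs gave fallback error of 4.9–6.1% at R² = 0, 3.9–4.1% at 0.1, 2.8–3.0% at 0.2 and 2.1–2.8% at 0.3.

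**The case against.** The strongest reply is that little harm can follow. The fallback errs on the safe side, is used only if another model fails, and sits in the adjusted analysis, while the calibrated ICU-stratified test is run regardless. The study was sized on a Mann-Whitney test at 80% power, and the fallback roughly delivers that. All of this stands.

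It is also fair that the effect depends on an R² the documents do not give, and that the plan never promised the power of rank analysis of covariance. A further point concerns the method being replaced. In 1,000 simulated trials per setting at R² = 0.3, a fixed-effect median regression with default standard errors rejected 9.3% under the null and had 84.6% power. If the planned mixed model behaves similarly, the fallback loses little power against it. That is only an approximation; the mixed model itself was not simulated.

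A reader might infer more than the text supports:

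- That the error rate is far below 5% in every case. It is nominal when the covariates are not prognostic.
- That the trial becomes underpowered or its positive findings unreliable. Neither follows from these figures.
- That the decisive primary result is affected. The SAP does not say that the adjusted analysis decides the trial.
- That ICU is dropped from the fallback. ICU is a listed covariate and so enters the score; whether ICU strata are also kept is not stated.
- That the regression is likely to fail. Many covariates and a bounded day count make failure conceivable, but its probability cannot be computed from the documents.

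None of this gives a reason to prefer the fallback. If the covariates are not prognostic it does nothing useful, and if they are it wastes most of their value.

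**Conclusion.** The point holds as a matter of efficiency and calibration in a contingency analysis. With covariate R² of 0.2–0.3, the fallback's true type I error is about 2–3%. Its power of about 80–85% is roughly that of the unadjusted ICU-stratified test, so nearly all of the 5–8 points available from direct adjustment are lost. At R² = 0.1 the error is only mildly low (about 3.5–4%), and at R² = 0 it is nominal.

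The direction follows from randomization and from the variance the test uses. The size rests on the assumed R², on assumed category counts for the covariates, and on a simulated outcome with the mean and SD quoted in Sample Size. An R² of 0.2 or more is plausible given that prior delirium and severity scores are listed, but it remains an assumption. The consequence is an adjusted p-value that is too large, with no excess of false positives.

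**What to change.** Replace the propensity-score fallback with rank analysis of covariance stratified by ICU. Use the listed covariates that are measured before or at randomization, and include need for tracheostomy only if it is known by then. State in the same sentence what counts as failure of the median regression, so that the switch is not a judgement made after seeing results.

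The cumulative-logit model that the SAP names for ordinal scales should not be written in as the substitute on the strength of this check, because its error rate and power were not examined.

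The cost is SAP wording and an adjusted estimate on the rank scale, which is less familiar to clinical readers than a difference in median days. No new data are needed. If the covariates turn out to explain nothing, direct adjustment gives up 82.6 − 79.9 = 2.7 points of power against the unadjusted test, about the same as the present fallback (82.6 − 79.3 = 3.3).
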